3.6.2 Clinical Laboratory Test Results

All clinical laboratory data will be stored on the database in the units in which they were reported. Patient listings and summary statistics at each assessment time will be presented using the International System of Units (SI units; Système International d'Unités). Laboratory data not reported in SI units will be converted to SI units before processing.

Laboratory test values will be presented by individual listings with flagging of values outside the normal ranges.

3.6.2.1 Standard Reference Ranges and Transformation of Data

Roche standard reference ranges, rather than the reference ranges of the Investigator or central lab, will be used for all parameters. For most parameters, the measured laboratory test result will be assessed directly using the Roche standard reference range. Certain laboratory parameters will be transformed to Roche's standard reference ranges.

A transformation will be performed on certain laboratory tests that lack sufficiently common procedures and have a wide range of Investigator ranges, e.g., enzyme tests that include AST, ALT, and alkaline phosphatase and total bilirubin. Given that the standard reference ranges for these parameters have a lower limit of zero, only the upper limits of the ranges will be used in transforming the data.

3.6.2.2 Definition of Laboratory Abnormalities

For all laboratory parameters included, there exists a Roche predefined standard reference range. Laboratory values falling outside this standard reference range will be labeled "H" for high or "L" for low in patient listings of laboratory data.

In addition to the standard reference range, a marked reference range has been predefined by Roche for each laboratory parameter. The marked reference range is broader than the standard reference range. Values falling outside the marked reference range that also represent a defined change from baseline will be considered marked laboratory abnormalities (i.e., potentially clinically relevant). If a baseline value is not available for a patient, the midpoint of the standard reference range will be used as the patient's baseline value for the purposes of determining marked laboratory abnormalities. Marked laboratory abnormalities will be labeled in the patient listings as "HH" for very high or "LL" for very low.

3.6.3 Vital Signs

Vital signs data will be presented by individual listings with flagging of values outside the normal ranges and flagging of marked abnormalities. In addition, tabular summaries will be used, as appropriate.

3.6.4 ECG Data Analysis

ECG data will be presented by individual listings with flagging of values outside the normal ranges and flagging of marked abnormalities. In addition, tabular summaries will be used, as appropriate.

3.6.5 Anti-Drug Antibody Data Analysis

The number and percentage of patients who test positive for plasma antibodies to RO6867461 at baseline and at the study visits will be tabulated, except for treatment arm A.

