1.2.1 Previous Non-Clinical Studies

Pharmacological studies were performed in vitro and in vivo to investigate the target binding affinity, specificity, and biological activity of RO6867461. In vitro studies demonstrated that RO6867461 binds the target molecules VEGF and Ang-2 with high affinity. Mutations in the Fc region of RO6867461 abolish binding to Fc_Y receptors, located on effector cells, and the neonatal Fc receptor (FcRn).

In the absence of a suitable model of DME, pharmacological evaluation in vivo focused on well characterized models of choroidal vessel edema and neovascularization. These evaluations demonstrated that RO6867461 reduces the formation of neovessels, the leakiness of existing CNV lesions, and subsequent injury to the retina due to lesion formation in a mutant mouse model of early bilateral CNV and a laser-induced model of CNV in cynomolgus monkeys (*RO6867461 Investigator's Brochure* Version 4).

RO6867461—F. Hoffmann-La Roche Ltd
22/Protocol BP30099, Version 3

In a 2-month Good Laboratory Practice (GLP) study in cynomolgus monkeys, ocular and extra-ocular findings occurred following three IVT injections of the highest 3 and 6 mg/eye/dose. The no observed adverse effect level (NOAEL) was established at a dose of 1.5 mg/eye/dose for IVT administration.

In a 6-month GLP study in cynomolgus monkeys, no changes were observed following seven IVT injections every 4 weeks at the low dose of 0.5 mg/eye/dose comprising the NOAEL. Dose-dependent ocular inflammatory cell infiltration and clinical signs of ocular inflammation occurred in RO6867461-treated eyes at 1.5 or 1.5/3 mg/eye/dose IVT following the same dosing schedule.

In both studies, findings generally correlated with the systemic presence of anti-drug antibodies (ADAs) against RO6867461 and exposure loss in the serum of animals. In addition, immunohistochemistry confirmed the presence of immune-complex deposits in RO6867461-treated animals with ocular and extra-ocular findings (in the 3-month study). Therefore, these effects were consistent with an immune-mediated response to a humanized antibody like RO6867461 in non-human primates.

RO6867461 did not induce any neurological (CNS) findings or effects on heart rate/electrocardiogram endpoints (including QT and QTc [corrected QT interval]), respiratory rate, or body temperature in cynomolgus monkeys up to 6 months treatment.

See the [RO6867461 Investigator's Brochure](#) for details on nonclinical studies.

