3.3 OUTCOME MEASURES

3.3.1 Safety Outcome Measures

The safety outcome measures for this study are as follows:

- Any relevant safety observations derived from BCVA (modified ETDRS charts), slit-lamp examination, dilated binocular indirect high-magnification ophthalmoscopy, intraocular pressure (IOP), fundus photography (FP), SD-OCT, and angiography
- Incidence and severity of ocular adverse events
- Incidence and severity of non-ocular adverse events
- Incidence of laboratory abnormalities, based on hematology, clinical chemistry, and urinalysis test results
- Incidence of anti-RO6867461 antibodies
- ECGs
- Vital signs

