4.3.1.1 Criteria for Treatment with Ranibizumab during Observational Period

At each visit following the last dose of study treatment (week 20 visit), BCVA will be assessed and SD-OCT imaging will be performed (except for week 26 visit).

BCVA and CST values obtained at week 24 will be compared to those obtained at visit week 20. BCVA and CST values obtained at weeks 28, 32 and 36 will be compared to those of week 24.

If the patient meets both of the following criteria the patient should receive a single dose of 0.3 mg ranibizumab and will exit the study:-

- CST increased by $\geq 50 \mu\text{m}$
- BCVA decreased by ≥ 5 letters due to DME

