4.6.7.4 Assessments at Final Visit

Patients will return to the investigational site every 4 weeks up to week 36 during observation period after their final dose of study drug at week 20.

If during any of these evaluations the patients meet the pre-specified criteria (see Section 4.3.1.1), the patients will receive a single dose of 0.3 mg ranibizumab, exit the study, and receive a follow up phone call 7 days after the dose of ranibizumab to evaluate any potential adverse events. Otherwise, patients will exit the study once they have completed the observational visit at week 36.

After the final visit, adverse events should be followed up as outlined in Section 5.6.

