Appendix 1 Schedule of Assessments (cont.)

Week	Screening	Week 1		Week 4	Week 8	Week 12	Week 16	Week 20	Week 24 ^t	Week 26 ^m	Week 28 ^t	Week 32 ^t	Week 36 ^t	Early Termination Visit	Unscheduled Visit
Dag	D-28 to D-1	Dag 1	Dag 7	Dag 28	Dag 56	Dag 84	Dag 112	Dag 140	Dag 168	Dag 182	Dag 196	Dag 224	Dag 252		
Time Relative (h)		0	144	648	1320	1992	2664	3336	4008	4344	4680	5352	6024		
Visit Window		+1-7	+1-7	+1-7	+1-7	+1-7	+1-7	+1-7	+1-7	+1-7	+1-7	+1-7	+1-7	+7	
Assessments															
PK Sample ^a		X	X	X		X		X	X	X	X ^{m,q}	X ^{m,q}	X ^q	X	X
PD Biomarkers Sample ^a		X	X	X		X			X	X	X ^q	X ^q	X ^q	X	X
Exploratory Plasma Biomarkers Sample ^a		X				X			X					X	X
Clinical Genotyping Sample ^{a,g,h}		X													
Anti-Drug Antibody ^{a,f}		X	X	X		X		X	X		X ^q	X ^q	X ^q	X	X
follow-up phone call ^l									X ^s		X ^s	X ^s	X ^s		
Adverse Events	X	X	X	X	X	X	X	X	X	X	X	X	X	X	X
Previous and Concomitant Treatments	X	X	X	X	X	X	X	X	X	X	X	X	X	X	X

^a Assessment prior to study drug or ranibizumab administration on days where treatment is administered

^b For females only

^c Assessment in study eye only; except at screening for imaging assessments (FP, EDI SD-OCT, FFA), where either eye has a potential to meet all eligibility criteria

^d Finger count vision assessment asap after, and within maximum of 15 min from study drug or ranibizumab administration

^e Performed prior to pupil dilation

^f █

^g At day 1 but can be done at any other visit if the sample not collected at baseline

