Appendix 1 Schedule of Assessments (cont.)

- ^h Mandatory, except in countries or at investigational sites where IRB/EC does not approve
- ⁱ [REDACTED]
- ^j [REDACTED]
- ^k Baseline assessments
- ^l *IOP to be performed in both study and fellow eye. At visits with either study drug or ranibizumab administration the assessment post-treatment administration is in the study eye only. If IOP \geq 30 mmHg at 30 (\pm 5) minutes post-treatment administration in the study eye, then IOP is measured again at 60 (\pm 10) minutes.*
- ^m [REDACTED]
- ⁿ At the discretion of the investigator abnormal values might be followed-up at an unscheduled visit
- ^o Optional at Day 1
- ^p *If a site has an unexpected issue, the patient's study treatment may be administered within 3 working days of the scheduled treatment visit with the Medical Monitor's permission. The interval between two administrations of study drug needs to be at least 21 days*
- ^q when this visit becomes the final visit
- ^r *If pre-specified criteria are met*
- ^s *If patient receives ranibizumab at that visit*
- ^t *Visit becomes final visit when patient receives 0.3 mg ranibizumab based on meeting pre-specified criteria*
- ^u *7 days after 0.3 mg ranibizumab administration (+/- 3 days)*

Appendix 2
Grading Scale for Assessment of Anterior Chamber Flare or Cells, Vitreal Hemorrhage Density, and Vitreous Cells

GRADING SCALE FOR ANTERIOR CHAMBER FLARE OR CELLS

Flare	
0	No protein is visible in the anterior chamber when viewed by an experienced observer using slit-lamp biomicroscopy; a small, bright, focal slit-beam of white light; and high magnification.
Trace	Trace amount of protein is detectable in the anterior chamber: This protein is visible only with careful scrutiny by an experienced observer using slit-lamp biomicroscopy; a small, bright, focal slit-beam of white light; and high magnification.
1+	Slight amount of protein is detectable in the anterior chamber: the presence of protein in the anterior chamber is immediately apparent to an experienced observer using slit-lamp biomicroscopy and high magnification, but such protein is detected only with careful observation with the naked eye and a small, bright, focal slit-beam of white light.

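### SAP 3.6.5 tabulates ADA prevalence by visit rather than the named incidence, and its Week 28 to 36 percentages would come from differently selected patients

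*SAP*

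**What the plan says.** Protocol 3.3.1 and SAP 1.2.1 list as a safety outcome "Incidence of anti-RO6867461 antibodies". Protocol 2.2 also makes the formation of these antibodies a secondary objective.

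The only ADA analysis described is in SAP 3.6.5: counts and percentages for those "who test positive for plasma antibodies to RO6867461 at baseline and at the study visits will be tabulated, except for treatment arm A". Protocol 6.6.5 has the same plan without the arm A exception. Neither text states a denominator, defines treatment-emergent positivity, or asks for a summary across visits.

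The schedule in protocol Appendix 1 takes ADA samples without condition on Day 1, Day 7 and at Weeks 4, 12, 20 and 24. At Weeks 28, 32 and 36 the sample carries note q: "when this visit becomes the final visit". Note t adds: "Visit becomes final visit when patient receives 0.3 mg ranibizumab based on meeting pre-specified criteria". The criteria are in protocol 4.3.1.1: "If the patient meets both of the following criteria the patient should receive a single dose of 0.3 mg ranibizumab". They are a CST rise of at least 50 µm together with a BCVA loss of at least 5 letters due to DME. For everyone else, protocol 4.6.7.4 says that "patients will exit the study once they have completed the observational visit at week 36".

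**The concern.** There are two separate problems.

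The first is the quantity. A percentage positive at a visit includes patients who were already positive at baseline, and it does not accumulate patients who are positive at one visit and negative at the next. It answers a different question from how many patients develop antibodies after dosing.

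The second is who is sampled late. After Week 24 a scheduled sample depends on the visit being the patient's last, and at Weeks 28 and 32 that is tied to an efficacy outcome. A table that runs on from Week 24 to Week 36 invites reading as a time course although the sampled group changes in kind from row to row. How many patients contribute to each late row also depends on each arm's durability, so the 1.5 mg and 6 mg arms are not comparable there.

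A reader is likely to look in this table for a link between antibodies and loss of effect. Protocol 1.2.1 reports that in the monkey studies "findings generally correlated with the systemic presence of anti-drug antibodies (ADAs) against RO6867461 and exposure loss in the serum of animals".

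**Working it through.** The documents give no ADA rate and no exit rate, so there is no planned figure to reproduce. The sampling follows from the text. The numbers below are illustrations with assumed rates.

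**1. Who contributes a scheduled sample** (protocol Appendix 1, notes q and t; protocol 4.3.1.1 and 4.6.7.4)

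| Visit | Condition | Patients sampled |
|---|---|---|
| Day 1, Day 7, Weeks 4, 12, 20, 24 | none | all attending |
| Weeks 28, 32 | final visit only | mainly those exiting on the worsening criteria |
| Week 36 | final visit only | all who did not exit earlier |

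**2. Prevalence against incidence.** There are five common post-dose visits: Day 7 and Weeks 4, 12, 20 and 24. Suppose 5% are positive at each, with none positive at baseline.
- Same patients each time: cumulative incidence 5%.
- Transient and independent between visits: 1 − (1 − 0.05)^5 = 22.6%.

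The by-visit table would look the same in both cases. This holds whether or not ADA has anything to do with exit.

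**3. Samples in the late rows.** Inputs: about 50 treatment-naïve patients in arm B, and about 50 + 30 = 80 in arm C (SAP 2.1). The 10% drop-out of protocol 6.1 is assumed to have occurred by Week 24 in both groups, leaving N = 45 and 72. A fraction h of those attending is assumed to exit at each of Weeks 24, 28 and 32, with h from 5% to 30%.
- Week 28 samples = N(1 − h)h. Arm B: 45 × 0.95 × 0.05 = 2.1, up to 45 × 0.70 × 0.30 = 9.4. Arm C: 3.4 to 15.1.
- Week 32 samples = N(1 − h)²h. Arm B: 2.0 to 6.6. Arm C: 3.2 to 10.6.
- Week 36 samples = N(1 − h)³. Arm B: 38.6 down to 15.4. Arm C: 61.7 down to 24.7.

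A once-per-patient summary keeps nearly the full arm, about 50 and 80.

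**4. Effect of selection on the percentage.** Let p be the true proportion positive among patients attending Week 28, and r the exit risk in positives relative to negatives. Among those sampled, the proportion positive is pr / (pr + 1 − p).

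| p | r = 1 | r = 2 | r = 3 |
|---|---|---|---|
| 5% | 5% | 9.5% | 13.6% |
| 10% | 10% | 18.2% | 25.0% |
| 20% | 20% | 33.3% | 42.9% |

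With r = 0.5 and p = 10%, the figure is 0.05 / (0.05 + 0.90) = 5.3%, so the direction can reverse.

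For Week 36, take p = 10% and an exit risk per visit of 10% in negatives and 20% or 30% in positives. The proportion positive among those left after Weeks 28 and 32 is 0.10 × 0.80² / (0.10 × 0.80² + 0.90 × 0.90²) = 8.1%, or 6.3% with 30%. The table would then go from 18.2–25.0% at Week 28 to 6.3–8.1% at Week 36 with nobody's status changed.

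**5. Precision and denominator.** One positive of five sampled has an exact 95% interval of 0.5% to 71.6%. If the denominator were instead the whole arm C safety population of 80, with 10% to 20% exiting per visit and r from 1 to 3, a true 10% at Week 28 would show as about 0.8% to 3.6%. The SAP does not say which denominator applies.

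**The case against.** The strongest reply is that this is a missing definition in a descriptive table. Everyone who stays in the study is sampled through Week 24 and again at exit, so incidence can be derived from data already planned. That is right. A reader might infer that conditional late sampling is what prevents incidence from being estimated. It is not. The two problems are independent, and the first is purely one of analysis definition.

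A reader might also infer that Weeks 28 and 32 contain only patients who lost effect. Scheduled samples come mainly from them, but ADA can also be drawn at unscheduled visits, SAP 3.4.1 lets such visits be windowed into scheduled ones, and note q does not restrict the reason for a final visit.

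Nor do the documents show that the late percentages will be inflated. Nothing in them links ADA to exit in patients. With no link, the Week 28 and 32 figures are unbiased but imprecise. Protocol 1.2.1 attributes the monkey findings to an immune response to a humanized antibody in non-human primates, so they are a reason to look and not evidence of a bias.

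It is tempting to extend the point to plasma VEGF and Ang-2, which carry the same note q at these visits. No by-visit analysis of those biomarkers is visible in the SAP and protocol 6.8 is redacted, so the extension is not supported.

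Finally, note f on the ADA row is redacted, and the list of planned outputs, which SAP 3.6 says holds all safety reports, is not among the documents. Either could add detail, including an incidence table. The wording of SAP 3.6.5 also does not expressly promise separate Week 28, 32 and 36 rows, although that is its natural reading. The SAP should still define the outcome that it names.

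**Conclusion.** The point stands as a minor one. As written, SAP 3.6.5 yields prevalence by visit and not the named incidence, and in step 2 the two differ by a factor of up to about 4.5 (22.6% against 5%). Percentages for Weeks 28 and 32 would rest on roughly 2 to 15 patients per arm under the assumed exit rates, mainly patients exiting for worsening. Week 36 would rest on those who did not exit earlier. These rows should not be read as a time course or compared between doses.

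The sampling pattern comes from the text. The sample counts rest on assumed exit rates, and the size and direction of any bias rest on a relation between ADA and exit that the documents do not give. The outcome is descriptive, with no test or decision rule attached, and the primary analysis is unaffected.

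**What to change.** In SAP 3.6.5, make the main ADA result the per-patient treatment-emergent incidence in each RO6867461 arm:
- Numerator: patients negative at baseline with at least one positive post-dose sample at any time up to and including the exit sample.
- Denominator: patients with a baseline sample and at least one post-dose sample.
- Report baseline positives separately.
- Show the result overall and by previous anti-VEGF status. Of the two RO6867461 arms only arm C includes previously treated patients, so the like-for-like dose comparison is in treatment-naïve patients.

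A second figure through Week 24, where sampling is common to all, may be added. It should not replace the main one, because it would miss antibodies first seen at the exit sample.

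Keep by-visit percentages through Week 24 and show the number tested. Pool the Week 28, 32 and 36 samples as one final-visit row, split into exit for worsening and Week 36 completion. State where a patient who meets the criteria at Week 36 is counted.

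The cost is SAP wording and changes to the ADA output, with no new samples. The loss is that there are no separate Week 28, 32 and 36 rows.

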3.6.6 Ocular Assessments

Results of the following ocular assessments will be summarized by time point for the study eye using descriptive summaries: BCVA (also for the non-study eye), IOP (also for the non-study eye), and changes from baseline in these measurements will be tabulated.

3.6.7 Concomitant Medications

The original terms recorded on the patients' eCRF by the Investigator for concomitant medications will be standardized by the Sponsor by assigning preferred terms.

RO6867461—F. Hoffmann-La Roche Ltd

Statistical Analysis Plan BP30099

Concomitant medications will be presented in summary tables and listings, separated into ocular and non-ocular categories.

3.6.8 Exposure to Study Medication

The following extent to study medication will be summarized by treatment arm:

- Duration of treatment, to be calculated as first day to last day to masked study medication
- Relative extent of exposure as number of given intravitreal injections divided by number of planned intravitreal injections of masked study medication during the treatment duration of a patient.

3.7 MISSING DATA

An analysis of the sensitivity of the assumptions on missing values may be performed for the primary efficacy variable.

The primary analysis assumes that the data are missing at random (MAR).

As a sensitivity analysis the LOCF imputation will be used in the analysis of the primary endpoint.

3.8 INTERIM ANALYSES

Given the hypothesis-generating nature of this study, the Sponsor may conduct up to two additional interim analyses of efficacy. The decision to conduct such an interim analysis and its timing will be documented in the Sponsor's study master file prior to the conduct of the interim analysis. The Clinical Study Report will also document that such an interim analysis occurred. The interim analysis, should it occur, will be performed and interpreted by members of the IMC and management who would then be unmasked at the treatment group level. Access to treatment assignment information will follow the Sponsor's standard procedures.

List of interim analysis outputs is described in the interim LoPO document.

APPENDIX 1

PROTOCOL SYNOPSIS

TITLE: A MULTIPLE-CENTER, MULTIPLE-DOSE, RANDOMIZED, ACTIVE COMPARATOR-CONTROLLED, DOUBLE-MASKED, PARALLEL GROUP, 36-WEEK STUDY TO INVESTIGATE THE SAFETY, TOLERABILITY, PHARMACOKINETICS, AND EFFICACY OF RO6867461 ADMINISTERED INTRAVITREALLY IN PATIENTS WITH DIABETIC MACULAR EDEMA

PROTOCOL NUMBER: BP30099

VERSION: 1

EUDRACT NUMBER: NA

IND NUMBER: 119,225

TEST PRODUCT: RO6867461

PHASE: II

INDICATION: Diabetic macular edema (DME)

SPONSOR: F. Hoffmann-La Roche Ltd

OBJECTIVES

Primary Objective

The primary objective of this study is:

To evaluate the efficacy of RO6867461 compared with the active comparator in *treatment naïve* patients with center-involving diabetic macular edema (CI-DME)

Secondary Objectives

The secondary objectives for this study are as follows:

- To assess the safety of multiple intravitreal (IVT) doses of RO6867461
- To assess systemic pharmacokinetics of RO6867461
- To investigate pharmacodynamics and anatomical outcomes informing on the mechanism of action of RO6867461
- To investigate the formation of plasma anti-RO6867461 antibodies
- To explore the duration of effect of RO6867461

Exploratory Objectives

The exploratory objectives for this study are as follows:

- *To explore the predictive effect of previous IVT anti-VEGF treatment on efficacy of RO6867461*
- *To evaluate the efficacy and safety of RO6867461 compared with the active comparator in patients with CI-DME with previous IVT anti-VEGF treatment.*

- [REDACTED]
- [REDACTED]
- [REDACTED]
- To evaluate improvement in diabetic retinopathy (DR) severity score

RO6867461—F. Hoffmann-La Roche Ltd
Statistical Analysis Plan BP30099

STUDY DESIGN

This is a multiple-center, multiple-dose, randomized, active comparator-controlled, double-masked, three parallel group, 36-week study in patients with CI-DME.

The three groups of this study are as follows:

- Arm A: 0.3 mg ranibizumab IVT
- Arm B: 1.5 mg RO6867461 IVT
- Arm C: 6 mg RO6867461 IVT

Only one eye will be selected as the study eye. Where both eyes meet all eligibility criteria, the eye with the worse BCVA will be defined as the study eye. Where both eyes meet all eligibility criteria and have the same BCVA letter score at Day 1, study eye selection is at the investigator's discretion.

NUMBER OF PATIENTS

Up to 210 patients will be randomized.

Approximately 150 treatment-naïve patients and approximately 60 patients who have been previously treated with IVT anti-VEGF will be enrolled in the study.

Approximately 50 treatment-naïve patients will be randomized on each arm (1:1:1 randomization scheme) and approximately 30 patients previously treated with IVT anti-VEGF will be randomized into arms A and C.

TARGET POPULATION

Male and female patients of ≥ 18 years of age with CI-DME.

INCLUSION/EXCLUSION CRITERIA

Inclusion Criteria

Patients must meet the following criteria for study entry:

Ocular criteria for study eye:

- Macular edema associated with DR defined as macular thickening by spectral domain optical coherence tomography (SD-OCT) involving the center of the macula: central subfield thickness (CST) of ≥ 325 μm with Spectralis (Heidelberg) at screening (where Spectralis is not available, the following devices and CST thresholds are acceptable: CST ≥ 315 μm for Cirrus, CST ≥ 315 μm for Topcon, CST ≥ 295 μm for Optovue).
- Decreased visual acuity attributable primarily to DME, with best corrected visual acuity (BCVA) letter score of 73–24 letters (inclusive) on Early Treatment Diabetic Retinopathy Study (ETDRS)-like charts (20/40–20/320 Snellen equivalent) on Day 1
- Clear ocular media and adequate pupillary dilatation to allow acquisition of good quality retinal images to confirm diagnosis

General criteria:

- Diagnosis of diabetes mellitus (DM; Type 1 or Type 2), as defined by the World Health Organization and/or American Diabetes Association
- Able and willing to provide written informed consent and to comply with the study protocol according to International Conference on Harmonization (ICH) and local regulations. Alternatively, a legally authorized representative must be able to consent for the patient according to ICH and local regulations.
- Age ≥ 18 years
- For women who are not postmenopausal (i.e. ≥ 12 months of non-therapy-induced amenorrhea, confirmed by FSH, if not on hormone replacement) or surgically sterile (absence of ovaries and/or uterus) agreement to remain abstinent or use combined contraceptive methods that result in a failure rate of $< 1\%$ per year during the treatment period and at least through 4 weeks after last dose.

Abstinence is only acceptable if it is in line with the preferred and usual lifestyle of the patient. Periodic abstinence (e.g., calendar, ovulation, symptothermal, or post ovulation methods) and withdrawal are not acceptable methods of contraception;

Examples of contraceptive methods with an expected failure rate of $< 1\%$ per year include male sterilization, hormonal implants, proper use of combined oral or

RO6867461—F. Hoffmann-La Roche Ltd

Statistical Analysis Plan BP30099

injected hormonal contraceptives, and certain intrauterine devices. Alternatively, two methods (e.g., two barrier methods such as a condom and a cervical cap) may be combined to achieve a failure rate of < 1% per year, barrier methods must always be supplemented with the use of a spermicide.

- For men: agreement to use a barrier method of contraception during the treatment period for at least 4 weeks after the last dose of study drug
- Patients must be willing not to participate in any other clinical trial including an investigational medical product (IMP) or device up to completion of the current study.

Exclusion Criteria

Patients who meet any of the following criteria will be excluded from study entry:

Ocular criteria for study eye:

- *Any signs of high-risk PDR defined as:*
 - *any vitreous or pre-retinal hemorrhage*
 - *NVE $\geq 1/2$ disc area within an area equivalent to the standard mydriatic ETDRS 7- field on clinical examination*
 - *NVD $\geq 1/3$ disc area on clinical examination*
- Any IVT anti-VEGF treatment within 3 months prior to Day 1
- Any panretinal photocoagulation (PRP) treatment prior to Day 1
- Any macular laser photocoagulation within 3 months prior to Day 1
- History of vitreoretinal surgery
- *Any IVT or periocular corticosteroid treatment within 3months prior to Day 1. Any history of Iluvien or Ozurdex implants prior to Day 1 will not be permitted*
- Any cataract surgery or treatment for complications of cataract surgery with steroids within 3 months prior to Day 1
- History of incisional glaucoma surgery
- Uncontrolled glaucoma (e.g., progressive loss of visual fields or defined as intraocular pressure [IOP] ≥ 25 mmHg despite treatment with anti-glaucoma medication)

Concurrent ocular conditions in the study eye:

- History of rubeosis
- Any current or history of ocular disease other than DME that may confound assessment of the macula or affect central vision (e.g., age-related macular degeneration, retinal vein occlusion, uveitis, angioid streaks, histoplasmosis, active or inactive cytomegalovirus, pathological myopia, retinal detachment, macular traction, macular hole, significant cataract)
- *Any current ocular condition for which, in the opinion of the investigator, visual acuity loss would not improve from resolution of macular edema (e.g., foveal atrophy, pigment abnormalities, dense sub-foveal hard exudates, non-retinal condition)*
- Any active ocular infection on Day 1
- Any active intraocular inflammation (grade trace or above) on Day 1

Characteristics for fellow eye:

- Any anti-VEGF treatment within 7 days prior to Day 1
- Any retinal condition that, in the opinion of the investigator, might require anti-VEGF treatment within 7 days from Day 1

General criteria:

- Any systemic anti-VEGF within 6 months prior to Day 1
- Any major illness or major surgical procedure within 1 month prior to Day 1
- Any febrile illness within 1 week prior to Day 1
- Any stroke or myocardial infarction within 12 months prior to Day 1

- Uncontrolled blood pressure (BP; defined as systolic > 180 mmHg and/or diastolic > 100 mmHg while patient at rest). If a patient's initial reading exceeds these values, a second reading may be taken *either 30 or more minutes later on the same day or on another day during the screening period*. If the patient's BP needs to be controlled by antihypertensive medication, the patient *should be taking the same medication continuously for at least 1 month prior to Day 1*.
- Patients with glycosylated hemoglobin HbA1c > 12% at screening
- Untreated diabetes mellitus or initiation of oral anti-diabetic medication or insulin within 4 months prior to Day 1 or anticipated change of anti-diabetic medications within the duration of the study
- Renal failure requiring renal transplant, hemodialysis, or peritoneal dialysis within 6 months prior to Day 1 or anticipated to require hemodialysis or peritoneal dialysis at any time during the study
- History of other disease, metabolic dysfunction, physical examination finding, or clinical laboratory finding giving reasonable suspicion of a condition that contraindicated the use of the IMP or that might affect interpretation of the results of the study or renders the patient at high risk for treatment complications in the opinion of the investigator
- For females of childbearing potential, a positive blood pregnancy test
- Lactating female
- Use of systemic corticosteroids within 1 month prior to Day 1
- Any known hypersensitivity to active comparator, fluorescein, any ingredient of the formulation used, dilating eye drops, or any anesthetics and microbial drops used
- Any other restriction accorded to the use of the active comparator
- Any treatment with an IMP in the 3 months prior to Day 1

LENGTH OF STUDY

The total duration of the study will be up to 40 weeks (from screening through study completion) for each enrolled patient as follows:

- Screening: up to 4 weeks
- Baseline: Day 1
- Study treatment administration *period*: from Day 1 to Week 20
- *Observational period: From Week 20 up to Week 36*
- *Safety follow up call: During the observational period and 7 days after ranibizumab administration*

END OF STUDY

The end of the study is defined as the date when the last patient last observation (LPLO) occurs. LPLO is expected to occur 36 weeks after the last patient is enrolled.

OUTCOME MEASURES

SAFETY OUTCOME MEASURES

The safety outcome measures for this study are as follows:

- Any relevant safety observations derived from BCVA (modified ETDRS charts), slit-lamp examination, dilated binocular indirect high-magnification ophthalmoscopy, IOP, fundus photography (FP), SD-OCT, and angiography
- Incidence and severity of ocular adverse events
- Incidence and severity of non-ocular adverse events
- Incidence of laboratory abnormalities, based on hematology, clinical chemistry, and urinalysis test results
- Incidence of anti-RO6867461 antibodies
- ECGs
- Vital signs

RO6867461—F. Hoffmann-La Roche Ltd

Statistical Analysis Plan BP30099

PHARMACOKINETIC OUTCOME MEASURES

Plasma Levels of RO6867461

Plasma concentrations will be measured by a validated ELISA method. The pharmacokinetic (PK) analysis is described in the statistical methods section in the protocol. Samples may also be analyzed for ranibizumab by an appropriate assay.

EFFICACY AND PHARMACODYNAMIC OUTCOME MEASURES

The primary analysis population will be treatment naïve patients. Additional analyses may be performed in the overall population and in patients previously treated with IVT anti-VEGF.

The primary efficacy outcome measure for this study is the mean change in BCVA (ETDRS letters) from baseline at Week 24 in treatment-naïve patients.

The secondary efficacy outcome measures for this study include functional (BCVA) and anatomical (PD imaging) measures relevant to the mechanism of action of RO6867461 as follows:

BCVA:

- Proportion of patients gaining ≥ 15 letters from baseline BCVA at Week 24
- Proportion of patients with BCVA ≥ 69 letters (20/40 or better) at Week 24
- Proportion of patients with BCVA ≥ 84 letters (20/20 or better) at Week 24

Anatomic outcome measures by SD-OCT:

- Mean change from baseline in foveal center point thickness at Week 24
- Mean change from baseline in mean CST (1 mm diameter) at Week 24
- Proportion of patients with resolution of subretinal and intraretinal fluid at Week 24

Anatomic outcome measures by fundus fluorescein angiography (FFA)

- Proportion of patients with resolution of leakage at the macula at Week 24
- Change from baseline in the size of the foveal avascular zone at Week 24

Plasma RD biomarker outcome measure

Plasma T-B biomarker outcome measure

EXPLORATORY OUTCOME MEASURES

EXPLORATORY OUTCOME MEASURES

The exploratory outcome measures for this study include but are not limited to the following:

PCVA

- *Difference in mean BCVA change from baseline between the treatment-naïve patients and patients with previous IVT anti-VEGF (differential effect of RO6867461)*
- *Proportion of patients with BCVA ≥ 69 letters (20/40 or better) over time*
- *Proportion of patients with BCVA ≥ 84 letters (20/20 or better) over time*

Disease-related exploratory outcome measure:

RO6867461—F. Hoffmann-La Roche Ltd
Statistical Analysis Plan BP30099

- Proportion of patients with DR severity improvement from baseline on the ETDRS-DRSS (diabetic retinopathy severity score) at Week 24

Anatomic exploratory outcome measures:

- Change from baseline in macular perfusion and leakage by FFA at Week 12
- Change from baseline in peripheral perfusion and leakage by FFA at Week 24

Durability-related exploratory outcome measures:

- *Time to increase of CST by $\geq 50\mu\text{m}$ and/or loss of ≥ 5 letters of BCVA due to DME compared to values at Week 20*
- *Time to treatment with 0.3 mg ranibizumab after Week 20*

[REDACTED]

[REDACTED]
[REDACTED]
[REDACTED]
[REDACTED]

BIOMARKER/GENOTYPING SAMPLE COLLECTION

Mandatory Biomarkers Samples

All patients who have been enrolled in the study will have mandatory PD and exploratory biomarker plasma samples taken at the time points indicated in the SoA. The PD and exploratory plasma samples will be collected to investigate biomarkers in plasma related to angiogenesis and diabetic disease biomarkers.

Clinical Genotyping Samples

A mandatory whole blood sample will be taken for DNA extraction from every patient. The DNA may be used to study genes related to DME, DR, and angiogenesis (e.g., VEGFA, VEGFR2, Ang-2, Tie-2, etc.) and the effect on the PK/PD/efficacy/safety of RO6867461. Data arising from this sample will be subject to the same confidentiality as other mandatory blood samples. This specimen will be destroyed up to 2 years after the final closure of the clinical database.

[REDACTED]

[REDACTED]
[REDACTED]
[REDACTED]
[REDACTED]

INVESTIGATIONAL MEDICINAL PRODUCT(S)

Test Product: RO6867461

Vials of sterile, colorless to brownish, preservative-free solution of RO6867461 (120 mg/mL) for IVT administration of either 1.5 mg or 6 mg dose every 4 weeks.

Placebo is provided as sterile, colorless to slightly brownish, preservative-free liquid, used only for dilution of RO6867461 drug product to the appropriate clinical dose.

A volume of 50 μ L will be administered by IVT injection for all study drugs tested in this study.

Comparator: ranibizumab

Ranibizumab (nominal content 0.3 mg/0.05 mL) required for completion of this study will be provided by the Sponsor as a solution formulated at 6 mg/mL and supplied as a single-use vial.

The double-masked design is achieved through strict independence of the pharmacist (or designated personnel) and investigators who are preparing and administering study drug, from the assessing investigators and remaining site personnel.

PROCEDURES

Detailed SoA and procedures are tabulated in Appendix 1 of the protocol.

Screening

